17.2 CORRECTION OUTCOME EVALUATION

The categorical variables to be described are, N and (%):

- According to the investigator, was the planned level of correction achieved? (Yes / No / Partially), if yes:
 - Please motivate the answer
 - Is another surgery recommended? (Yes / No)

The descriptive statistic (Mean, SD, Median, Q₁, Q₃, Min, Max) will be shown for the following continuous variables:

- Degree Varus
- Degree Valgus
- Degree antecurvature

18 DISCHARGE VISIT

18.1 DISCHARGE VISIT INFORMATION

The descriptive statistic (Mean, SD, Median, Q₁, Q₃, Min, Max) will be shown for the following continuous variable:

- Time from surgery to Discharge (days) (calculated as Date of discharge minus date of surgery)

The categorical variable to be described is, N and (%):

- Time from surgery to Discharge (days) within the time windows estimated in the protocol (5-9 days)? (Yes / No)

18.2 ROM AND WB AT DISCHARGE

The categorical variable to be described is, N and (%):

- Discharge Weight-bearing Grade (Non-weight-bearing (NWB) / Toe-touch weight-bearing (TTWB) / Partial weight-bearing (PWB) / Full weight-bearing (FWB))

The descriptive statistic (Mean, SD, Median, Q₁, Q₃, Min, Max) will be shown for the following continuous variables:

- ROM Knee Flexion
- ROM Knee Extension
- ROM Hip Flexion
- ROM Hip Extension
- ROM Hip Abduction

- ROM Hip Internal Rotation
- ROM Hip External Rotation
- ROM Ankle Joint Dorsiflexion
- ROM Ankle Joint Plantarflexion

19 FIRST CONTROL VISIT

19.1 VISIT GENERAL INFORMATION

The descriptive statistic (Mean, SD, Median, Q₁, Q₃, Min, Max) will be shown for the following continuous variable:

- Time from surgery to First control visit (days) (calculated as Date of first control minus date of surgery)

The categorical variable to be described is, N and (%):

- Time from surgery to First control visit (days) within the time windows estimated in the protocol (4-8 weeks)? (Yes / No)

The categorical variables to be described are, N and (%):

- Has the bone reached a satisfactory consolidation? (No / Partially / Yes)
- Comments

The categorical variables to be described are, N and (%):

- Did the patient refer pain at the treated limb ? (Not at all / A little bit / Moderately /Quite a bit /Extremely)
- In case of previous question is not equal to 'Not at all' VAS will be described
- In case of previous question is not equal to 'Not at all' VAS Pain Score according to the patient will be described
- X-ray AP image
- X-ray ML image

19.2 CORRECTION EVALUATION AT FIRST CONTROL

The categorical variables to be described are, N and (%):

- According to the investigator is the level of correction maintained? (No / Partially / Yes), if yes:
 - Please motivate the answer
 - Is another surgery recommended? (Yes / No)

The descriptive statistic (Mean, SD, Median, Q₁, Q₃, Min, Max) will be shown for the following continuous variables:

- Degree Varus
- Degree Valgus
- Degree antecurvature

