24.2 MAINTAINED BONE CORRECTION

This analysis will be performed for cases that have indicated: Deformity Correction.

The categorical variables to be described are:

- Number of Implants that according to the investigator is the level of correction maintained until last visit performed
- Number of Patients that according to the investigator is the level of correction maintained until last visit performed

A list with maintained bone correction variables will be shown.

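### SAP 17.2, 19.2, 20.2 and 21.3 restrict the reason and the further-surgery recommendation to implants rated Yes, so no summary table gives them for No or Partially

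*SAP*

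**What the plan says.** Four SAP sections describe the investigator's view of the correction, one per visit. At surgery (17.2) the line reads "According to the investigator, was the planned level of correction achieved? (Yes / No / Partially), if yes". At first control (19.2) it reads "According to the investigator is the level of correction maintained? (No / Partially / Yes), if yes", and the bone-consolidation (20.2) and device-removal (21.3) sections repeat that line unchanged. In each section the same two items are nested under the condition: the investigator's reason for the answer, and "Is another surgery recommended? (Yes / No". All are to be described with N and %.

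The only other output on the same subject is in SAP 24.2, which counts implants and patients with correction maintained and adds: "A list with maintained bone correction variables will be shown". That section is limited in scope: "This analysis will be performed for cases that have indicated: Deformity Correction".

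**The concern.** The condition selects the answer for which an explanation and a recommendation to operate again are least expected, and passes over the two for which they are most expected. A programmer who follows the text will produce a recommendation table for implants whose correction was achieved or maintained, and none for the others.

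Maintained alignment is one of the study's two efficacy endpoints (Protocol 6.2, SAP 7), and the study is meant to confirm the benefit/risk ratio (Protocol 5.2). When correction is lost or incomplete, the natural next questions are why, and whether a further operation was advised. As written, the tables answer neither for those implants.

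**Working it through.** The plan states no figure for this item and none can be recomputed, so the check is textual, with one short piece of algebra to bound the effect.

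**Step 1. The four sections side by side.**

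| SAP section | Visit | Parent question, answers offered | Answers for which the reason and recommendation are specified |
|---|---|---|---|
| 17.2 | Surgery | Correction achieved: Yes, No, Partially | Yes only |
| 19.2 | First control | Correction maintained: No, Partially, Yes | Yes only |
| 20.2 | Bone consolidation | Correction maintained: No, Partially, Yes | Yes only |
| 21.3 | Device removal | Correction maintained: No, Partially, Yes | Yes only |

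The condition appears in 4 of 4 sections.

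**Step 2. Comparison with another filter in the same SAP.** For pain, the follow-up score is tied to the adverse answers: "In case of previous question is not equal to 'Not at all' VAS will be described" (19.1, with the same rule in 20.1 and 21.1). The SAP can therefore express a filter that keeps the unfavourable responses. The correction items do the reverse.

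**Step 3. Search for the same information elsewhere.**
- SAP 24.2 gives counts of maintained correction and a listing. The listing does not name the surgery recommendation, covers deformity-correction cases only, and is not a summary with N and %.
- SAP 23.1 to 23.1.4 tabulate and list adverse events. Nothing says that a recommendation for further surgery is itself recorded as one.
- The protocol has no rule on reporting recommended further surgery, and its visit descriptions (10.2.1 to 10.2.6) do not mention the item.

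No specified summary table gives the recommendation for No or Partially.

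**Step 4. What the omission can and cannot do.** At one visit, let n_Y, n_P and n_N be the implants rated Yes, Partially and No, and r_Y, r_P and r_N those among them with another operation recommended.
- Specified output: r_Y out of n_Y.
- Complete output: r_Y + r_P + r_N out of n_Y + n_P + n_N.
- Omitted count: r_P + r_N, which lies between 0 and n_P + n_N.

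The parent table gives n_P + n_N, so a reader of the report could see the upper limit of what is missing but not the count. The documents give no value for any of these quantities, so the range cannot be narrowed.

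**The case against.** The strongest case on the other side is that this is a minor clarification.

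- **The item is not an endpoint.** The safety endpoints are device-related adverse events and device deficiencies; the performance endpoints are consolidation and maintained alignment. A reader might infer that a key failure outcome is being suppressed, but the documents do not give the recommendation that status, and no endpoint or confidence interval uses it. This stands and limits the weight of the point.
- **Failed corrections are not hidden.** A reader might infer that implants rated No or Partially drop out of the tables. They do not: the parent question is described for all three answers at every visit, and only the two nested items are lost. This stands.
- **There is partial cover elsewhere.** The 24.2 listing may show individual recommendations. An untoward event that leads to hospitalization, or to surgery to prevent permanent impairment, would meet the SAE definition (Protocol 11.1.2) and be tabulated. Both routes are uncertain: the listing does not say so, and the second depends on the investigator recording an event.
- **The table need not be nearly empty.** A reader might infer that restricting to Yes will show almost no recommendations. The documents do not support that. They do not define what counts as another surgery, each implant is followed to a second operation for plate removal (Protocol 7.3), and a patient may have several implants. A Yes rating together with a further recommended operation is plausible.
- **It may be one copied slip.** Three of the four lines are identical and the fourth nearly so, so repetition does not show intent. The governing CRF, v.96.11 (SAP 3), is not available. If it asks the item of everyone, the wording is a slip that programming might expose; if it branches on Yes, the fault is in data collection. The documents cannot settle which.

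None of this makes the written rule correct. It is not a missing detail but a stated condition that, if followed, gives a selective output.

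**Conclusion.** The point holds as a defect in a descriptive, supportive output. In all four correction sections the reason and the further-surgery recommendation are specified only for implants rated Yes, and no other summary table supplies them for No or Partially. The primary safety endpoint and the counts of consolidation and maintained correction are unaffected.

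The size of the effect cannot be stated: it depends on how many implants are rated No or Partially and how many of those carry a recommendation, and the documents give neither. The conclusion rests on reading the condition literally and on the 24.2 listing not being a substitute for a table. Whether the origin is the SAP text or the CRF branch remains open.

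The point is still worth acting on because only eCRF data enter the analysis (Protocol 14.6) and anomalies found in result tables will not by themselves reopen the database (SAP 15).

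**What to change.** 1. Delete the condition in SAP 17.2, 19.2, 20.2 and 21.3. Report the further-surgery recommendation as N and % over all implants assessed at the visit, cross-classified by Yes, Partially and No, and show the reasons at least for Partially and No.
2. Do not simply reverse the filter to No or Partially. That would exchange one selective table for another and lose recommendations among implants rated Yes.
3. Check the branch in CRF v.96.11 before database lock. If the item was asked of all implants, the text edit is enough. If it was asked only after Yes, say so as a limitation in the report, and label the blanks as not asked so that they do not enter the total percentage (SAP 14) as ordinary missing values.

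The cost is slightly more tabulation and one CRF check. If the CRF is at fault, a SAP edit cannot recover the answers. Time may also be short: the SAP was signed in April 2024, and the protocol synopsis anticipated database closure in 2Q 2024. In that case the limitation statement is the realistic remedy.

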19.3 ROM AND WB AT FIRST CONTROL

The categorical variable to be described is, N and (%):

- Current Weight-bearing Grade (Non-weight-bearing (NWB) / Toe-touch weight-bearing (TTWB) / Partial weight-bearing (PWB) / Full weight-bearing (FWB))

The descriptive statistic (Mean, SD, Median, Q₁, Q₃, Min, Max) will be shown for the following continuous variables:

- ROM Knee Flexion
- ROM Knee Extension
- ROM Hip Flexion
- ROM Hip Extension
- ROM Hip Abduction
- ROM Hip Internal Rotation
- ROM Hip External Rotation
- ROM Ankle Joint Dorsiflexion
- ROM Ankle Joint Plantarflexion

20 BONE CONSOLIDATION VISIT

20.1 VISIT GENERAL INFORMATION

The descriptive statistic (Mean, SD, Median, Q₁, Q₃, Min, Max) will be shown for the following continuous variable:

- Time from surgery to Bone Consolidation visit (months) (calculated as Date of bone consolidation minus date of surgery)

The categorical variable to be described is, N and (%):

- Time from surgery to Bone Consolidation visit (months) within the time windows estimated in the protocol (6-9 months)? (Yes / No)

The categorical variables to be described are, N and (%):

- Has the bone reached a satisfactory consolidation? (No / Partially / Yes)
- Comments

The categorical variables to be described are, N and (%):

- Did the patient refer pain at the treated limb ? (Not at all / A little bit / Moderately /Quite a bit /Extremely)
- In case of previous question is not equal to 'Not at all' VAS will be described
- In case of previous question is not equal to 'Not at all' VAS Pain Score according to the patient will be described
- X-ray AP image
- X-ray ML image

20.2 CORRECTION EVALUATION AT BONE CONSOLIDATION ASS

The categorical variables to be described are, N and (%):

- According to the investigator is the level of correction maintained? (No / Partially / Yes), if yes:
 - Please motivate the answer
 - Is another surgery recommended? (Yes / No)

The descriptive statistic (Mean, SD, Median, Q₁, Q₃, Min, Max) will be shown for the following continuous variables:

- Degree Varus
- Degree Valgus
- Degree antecurvature

20.3 ROM AND WB AT BONE CONSOLIDATION ASS

The categorical variable to be described is, N and (%):

- Current Weight-bearing Grade (Non-weight-bearing (NWB) / Toe-touch weight-bearing (TTWB) / Partial weight-bearing (PWB) / Full weight-bearing (FWB))

The descriptive statistic (Mean, SD, Median, Q₁, Q₃, Min, Max) will be shown for the following continuous variables:

- ROM Knee Flexion
- ROM Knee Extension
- ROM Hip Flexion
- ROM Hip Extension

- ROM Hip Abduction
- ROM Hip Internal Rotation
- ROM Hip External Rotation
- ROM Ankle Joint Dorsiflexion
- ROM Ankle Joint Plantarflexion

21 DEVICE REMOVAL VISIT

21.1 VISIT GENERAL INFORMATION

The descriptive statistic (Mean, SD, Median, Q₁, Q₃, Min, Max) will be shown for the following continuous variable:

- Time from surgery to Device removal visit (months) (calculated as Device Removal Surgery Date minus date of surgery)

The categorical variable to be described is, N and (%):

- Time from surgery to Device removal visit (months) within the time windows estimated in the protocol (10-18 months)? (Yes / No)

The categorical variables to be described are, N and (%):

- Has the bone reached a satisfactory consolidation? (No / Partially / Yes)
- Comments

The categorical variables to be described are, N and (%):

- Did the patient refer pain at the treated limb ? (Not at all / A little bit / Moderately /Quite a bit /Extremely)
- In case of previous question is not equal to 'Not at all' VAS will be described
- In case of previous question is not equal to 'Not at all' VAS Pain Score according to the patient will be described

21.2 DEVICE REMOVAL SURGERY INFORMATION

The descriptive statistic (Mean, SD, Median, Q₁, Q₃, Min, Max) will be shown for the following continuous variable:

- Duration surgery

The descriptive statistic (Mean, SD, Median, Q₁, Q₃, Min, Max) will be shown for the following continuous variable by the number of plates were applied during device **application** surgery:

- Duration surgery (hours)

Comparisons will be performed for this variable described above based on the number of plates using T-Student or U Mann Whitney, ANOVA or Kruskal Wallis, depending on the distribution of the variable.

The descriptive statistic (Mean, SD, Median, Q₁, Q₃, Min, Max) will be shown for the following continuous variable by MDD (Yes / No)¹ present in device removal visit:

- Duration surgery (hours)

Comparisons will be performed for this variable described above based on MDD at surgery using T-Student or U Mann Whitney depending on the distribution of the variable.

¹This variable will be obtained from Form MDD Description.

The categorical variable to be described is, N and (%):

- Did the patient receive a blood transfusion? (Yes / No)

The descriptive statistic (Mean, SD, Median, Q₁, Q₃, Min, Max) will be shown for the following continuous variable:

- Radian dose

The categorical variables to be described are, N and (%):

- Post removal AP projection X-Ray
- Post removal ML projection X-Ray

21.3 CORRECTION EVALUATION AT DEVICE REMOVAL

The categorical variables to be described are, N and (%):

- According to the investigator is the level of correction maintained? (No / Partially / Yes), if yes:
 - Please motivate the answer
 - Is another surgery recommended? (Yes / No)

The descriptive statistic (Mean, SD, Median, Q₁, Q₃, Min, Max) will be shown for the following continuous variables:

- Degree Varus
- Degree Valgus
- Degree antecurvature

21.4 ROM AND WB AT DEVICE REMOVAL

The categorical variable to be described is, N and (%):

- Current Weight-bearing Grade (Non-weight-bearing (NWB) / Toe-touch weight-bearing (TTWB) / Partial weight-bearing (PWB) / Full weight-bearing (FWB))

The descriptive statistic (Mean, SD, Median, Q₁, Q₃, Min, Max) will be shown for the following continuous variables:

- ROM Knee Flexion
- ROM Knee Extension
- ROM Hip Flexion
- ROM Hip Extension
- ROM Hip Abduction
- ROM Hip Internal Rotation
- ROM Hip External Rotation
- ROM Ankle Joint Dorsiflexion
- ROM Ankle Joint Plantarflexion

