EXCLUSION CRITERIA	
A patient will be excluded from participation in the study if he/she:
 
 • had/has a medical condition that is a contraindication according to the manufacturer's instruction for use leaflet; • had/has a concomitant not permitted device which cannot be safely removed; • patient for whom there are other concurrent medical or other conditions that in the opinion of the participating investigator may prevent participation or otherwise render patient ineligible for the study.
COMPARATIVE DEVICE	Not applicable (the study is not controlled)
PERMITTED CONCOMITANT DEVICE	K-wires and any other concomitant devices, i.e. bone screws, that were applied to fix any bone fragments but that were not considered critical for the maintenance of treated bone alignment, are permitted during the treatment. It is understood that any necessary medical devices applied on any other bones other than the one treated by JPS are permitted as well.
QUALITY OF LIFE (QOL)	
A QOL questionnaire is not performed in the normal clinical practice of the site participating this study. Provided clinical data will be retrospectively collected, it will not be possible to report a QOL questionnaire as a study result. Anyway, when available, the range of motion (ROM) of the treated limb and the weight bearing index will be collected and assessed as representative variables for the evaluation of the QOL of the enrolled Subjects.

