10.2.3 V2 (1 Week +/- 2 days): Hospital discharge

The investigator to collect information regarding changes in the concomitant medication, WBI; ROM (when available in the medical file) AEs and MDDs, if any.

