10.2.4 V3 (6 Weeks +/- 2 weeks): 1st control visit

The investigator will collect information regarding changes in the concomitant medication, AEs and MDDs, if any, about the functional recovery of the treated limb (by the means of the ROM and the WBI when available), and about the bone healing consolidation by X-ray images.

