auditor and regulatory authorities, and that the information will be used during the analysis of the results.

The data gathered for this group at the visits and assessment during the follow-up period, will be systematically collected by the investigator in eCRF.

Subjects will not undergo additional visits nor invasive or burdensome procedures additional to those already performed under the normal clinical practice. The scope of data collection is limited to the available data in the patients' charts.

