16.7 PRE-OP ROM AND WB BY IMPLANT

The categorical variables to be described are, N and (%):

- Pre operative Weight-bearing Grade (Non-weight-bearing (NWB) / Toe-touch weight-bearing (TTWB) / Partial weight-bearing (PWB) / Full weight-bearing (FWB))
- Which Range of Motion are available for this patient?
 - Knee Flexion
 - Knee Extension
 - Hip Flexion
 - Hip Extension
 - Hip Abduction
 - Hip Internal Rotation
 - Hip External Rotation
 - Ankle Joint Dorsiflexion
 - Ankle Joint Plantarflexion
 - None

The descriptive statistic (Mean, SD, Median, Q₁, Q₃, Min, Max) will be shown for the following continuous variables:

- ROM Knee Flexion
- ROM Knee Extension
- ROM Hip Flexion
- ROM Hip Extension
- ROM Hip Abduction
- ROM Hip Internal Rotation
- ROM Hip External Rotation
- ROM Ankle Joint Dorsiflexion
- ROM Ankle Joint Plantarflexion

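### Range of motion is summarised visit by visit, without n or paired change from pre-op, so a difference between visit means may reflect who was measured rather than recovery

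*SAP*

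**What the plan says.** **Purpose.** At the first control visit the protocol (10.2.4) collects information "about the functional recovery of the treated limb (by the means of the ROM and the WBI when available"; 10.2.5 and 10.2.6 give ROM the same role at bone consolidation and device removal. The synopsis explains that no quality-of-life questionnaire is used, and that ROM and weight bearing "will be collected and assessed as representative variables for the evaluation of the QOL of the enrolled Subjects".

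**Completeness.** At discharge the protocol asks for "ROM (when available in the medical file"), and 13.2 adds: "The scope of data collection is limited to the available data in the patients' charts".

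**Analysis.** SAP 16.7 records pre-operatively "Which Range of Motion are available for this patient" and then summarises nine movements by implant. The same nine recur at discharge (18.2), first control (19.3, for example "ROM Hip Flexion"), bone consolidation (20.3) and removal (21.4, for example "ROM Knee Flexion"). Each section gives mean, SD, median, quartiles and range for that visit alone.

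**Statistics listed.** Protocol 12.4 includes n among the summaries for quantitative variables. SAP 14 does not, and its paired total and valid percentage columns apply only to qualitative variables.

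**The concern.** Recovery is a change within a limb. The plan tabulates a pre-operative value and four later values for each movement, but never links them for the same implant. A reader who wants to know whether motion recovered must subtract one visit mean from another. That is sound only if the same implants stand behind both means, and the protocol expects ROM to be incomplete. With n absent from the SAP's list, the reader may not even see that the two sets differ in size.

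What is at stake is one of the two variables the protocol offers in place of a quality-of-life measure. The tables could suggest a gain or a loss that no measured limb had, or hide a real one.

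**Working it through.** The documents state no ROM mean, SD, effect or availability rate, so there is no figure of the plan's own to reproduce. The check is a reading of the text followed by two illustrations on assumed values.

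**1. Is ROM linked across visits anywhere in the SAP?**

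| SAP section | Content | ROM linked across visits? |
|---|---|---|
| 14 | Descriptive statistics; tests for independent samples | No |
| 16.7, 18.2, 19.3, 20.3, 21.4 | ROM at one visit each | No |
| 17.1, 21.2 | Group comparisons of surgery duration | No |
| 24.1, 24.2 | Consolidation and correction across visits | No |
| 24.3 | Weight bearing across visits, with time to full weight bearing | No |

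No section defines a change from pre-op or a set of implants with ROM at both times.

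**2. When is the difference of visit means enough?** If the same implants are measured at both visits, mean(post) − mean(pre) equals the mean of (post − pre). Even then the spread of change is missing: its variance is s_pre² + s_post² − 2·r·s_pre·s_post, and the visit tables do not give r. If those measured later are a subset of those measured pre-op, then

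difference of visit means = mean paired change + (pre-op mean of the subset − pre-op mean of all measured pre-op).

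The second term is pure selection.

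**3. Illustration A (assumed).** Thirty implants have pre-op hip flexion averaging 90 degrees. At removal only the 10 stiffer ones are measured; they averaged 75 before and gained 10.

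- Visit tables: 90, then 75 + 10 = 85, an apparent change of −5.
- Paired change in the 10: +10.
- Check: 10 + (75 − 90) = −5.

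**4. Illustration B (assumed, no implant changes).** Two equal strata differ by D degrees. The better stratum has availability a at both visits; the worse has b before and c at removal. Taking the better stratum as zero, the apparent change is

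−D·c/(a + c) + D·b/(a + b).

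| a; b to c | D = 10 | D = 20 | D = 30 |
|---|---|---|---|
| 0.8; 0.8 to 0.6 | 0.7 | 1.4 | 2.1 |
| 0.8; 0.8 to 0.4 | 1.7 | 3.3 | 5.0 |
| 0.6; 0.9 to 0.3 | 2.7 | 5.3 | 8.0 |

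Example: D = 20 with 0.8 to 0.4 gives −20 × 0.4/1.2 + 20 × 0.8/1.6 = −6.7 + 10 = 3.3. The mean paired change is zero in every cell.

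**The case against.** The strongest reply is that ROM is neither a safety nor an efficacy endpoint. It is chart data taken where it exists; protocol 12.4 promises descriptive statistics, and the SAP supplies them. No passage promises change from baseline. This stands, and it sets the weight of the point: a low-cost improvement to a supportive variable.

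It is also true that the illustrations are constructed and that complete pairs are themselves selected: +10 in 10 implants does not describe all 30. Deformity and fracture cases are mixed, and a pre-op value may not mean the same in both. Nine movements at three visits make 9 × 3 = 27 change summaries from some 30 to 40 implants. These are reasons to label the paired results carefully. They do not make the unpaired visit means a better guide.

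Several stronger readings are tempting and are not supported:

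- *Functional recovery goes unanalysed.* The protocol assigns that role to ROM and weight bearing together, and SAP 24.3 follows weight bearing across visits. The gap is in ROM.
- *Pre-op ROM is never used.* SAP 16.7 summarises it; it is just not linked to later values.
- *Each visit mean does come from a different set.* It can; no availability rates are given.
- *Pooling over treated bones puts hip motion of tibial cases into the hip averages.* Nothing shows that hip ROM is recorded for tibial cases. The target is the treated limb, and protocol 12.4 names anatomical site among the factors for which it declines subgroup summaries because of the small sample.
- *Pairing brings a large gain in precision.* In Illustration A with an assumed SD of 20 and correlation of 0.6, treating the means as independent gives sqrt(400/30 + 400/10) = 7.3. But the 10 are among the 30, so the covariance is 10 × 0.6 × 400/(30 × 10) = 8, and the SE is sqrt(13.33 + 40 − 16) = 6.1, against 20 × sqrt(2 × 0.4)/sqrt(10) = 5.7 paired. The case rests on selection, not precision.

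**Conclusion.** The point holds as a minor one. Followed exactly, the SAP never yields a within-implant result for ROM, although the protocol collects ROM to inform on recovery. A difference between visit means may reflect a changing set of implants, and the SAP's list drops the n that would alert a reader to this.

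The size cannot be determined from the documents. Under the assumed patterns above, selection alone moves the means by 0.7 to 8.0 degrees, and in one constructed case turns a gain of 10 into an apparent loss of 5. With complete ROM at every visit this bias would vanish, leaving only the spread of change unreported. The primary safety conclusion and the two efficacy endpoints are not touched.

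**What to change.** - In SAP 19.3, 20.3 and 21.4, the visits at which the protocol speaks of functional recovery, add for each ROM movement the change from pre-op in implants with both values: number of pairs, mean, SD, median, Q1, Q3, minimum and maximum.
- Show n beside every ROM visit summary (16.7, 18.2, 19.3, 20.3, 21.4), and add n to the quantitative list in SAP 14 so that it agrees with protocol 12.4.
- State with the tables that the paired set is a subset of the implants, and that pre-op ROM in fracture cases may not be a meaningful baseline.

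No restriction by treated bone is needed. The cost is a few derived variables and table rows from data already planned for the eCRF; the downside is more output on a variable that is not an endpoint.
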